6.3.1.2 Efficacy Analysis based on Treatment Policy Strategy

A supportive efficacy analysis will be performed by including all bleeding episodes collected through the end of the study, regardless of any premature treatment discontinuation, excluding only events due to major or minor surgeries based on ITT Analysis Set as in the primary analysis. The same negative binomial model as in the primary analysis will be used. It assesses the benefits of the fitusiran treatment policy strategy relative to on-demand treatment.

A sensitivity analysis to the above treatment policy analysis will be performed by including all bleeding events (ie, not excluding bleeding events due to surgeries).

Missing data sensitivity analyses using controlled imputation

The above efficacy analysis assumes the uncollected bleeding events after study discontinuation are missing at random (MAR). Sensitivity analyses will be performed to assess the robustness of this treatment policy analysis by imputing the missing data based on different missing data mechanism. The missing data will be imputed using multiple imputation (MI) methods for recurrent event data based on pattern mixture models (Keene et al, 2014) to assess the impact of different assumptions about the statistical behavior of post-withdrawal outcomes. The

post-withdrawal part of each pattern-specific distribution will be modelled using MAR and Copy Reference (CR) approaches. The MI will be carried out in the following steps:

1. Fit a Bayesian negative binomial model with a non-informative prior to the observed data with same set of covariates as in the primary analysis and obtain the posterior distributions of the event rate for both treatment arms.
2. Draw 100 independent samples from the conditional distribution of missing counts given the observed count and period of each patient with missing data based on different post-withdrawal imputation models, described below, for the treatment arms. The conditional distribution is also negative binomial.
3. The observed counts and imputed counts for each patient with missing data are summed.
4. Each 100 imputed datasets will then be analyzed using the same negative binomial regression model. Estimates from the model such as least squares means and standard errors are then combined across imputation datasets using Rubin's formula, as implemented in the MIANALYZE procedure. These and their 95% confidence interval limits are then exponentiated to obtain the estimate of ABR for each arm and the estimate of the ABR ratio and associated p-value.

MAR and CR approaches are described below:

1. Missing at Random (MAR) Approach: Post-withdrawal missing bleeding events in both fitusiran arm and on-demand arm will be imputed under the randomized arm.
2. Copy Reference (CR) Approach: The expected ABR for a patient in the fitusiran arm both pre- and post-withdrawal is assumed to be the same as that in the on-demand arm. This accounts for a gradual loss of fitusiran effectiveness post-withdrawal. If a patient in fitusiran arm has more events pre-withdrawal than expected if this patient had been in the on-demand arm, then this 'positive residual' will feed through into a higher than expected ABR in the post-withdrawal period. This is because this patient's earlier observed ABR higher than mean event rate suggests the patient has a higher propensity to have events. Post-withdrawal data in the on-demand arm are imputed under randomized arm (assumes MAR approach).

The efficacy analysis based on treatment policy strategy may serve as sensitivity analyses for the primary efficacy analysis based on on-treatment strategy. It is important to note that the estimand based on on-treatment strategy (the primary efficacy analysis) is considered most relevant and applicable in assessing and reporting clinical efficacy of fitusiran vs. on demand treatment.

Per-protocol analysis

Efficacy analysis will be repeated on the per-protocol analysis set as defined in [Section 4](#).

Zero-inflated negative binomial model

To address the concern of potential excessive zero bleeding events, the above on-treatment and treatment policy efficacy analyses will be repeated using the zero-inflated negative binomial model and the results will be presented if model converges.

Covid-19 related sensitivity analysis

To address the impact of Covid-19, the above on-treatment and treatment policy efficacy analyses in the treatment and efficacy periods will be repeated on the Covid-19 unaffected set as defined in [Section 4](#). In addition, a sensitivity analysis based on on-treatment strategy will be performed excluding the bleeding events in the period of missing at least two fitusiran doses in consecutive scheduled visits due to Covid-19 which is defined as one month after last dose (ie, last dose date + 28 days) before missing doses due to Covid-19 to one month after starting of re-dosing (ie, first re-dose date + 28 days). The same negative binomial model as in the primary analysis will be used.

6.3.1.3 Exploratory Analysis**All bleeding episodes (treated or untreated)**

The on-treatment and treatment policy efficacy analyses will be performed by including all bleeding episodes, regardless of administration of factor concentrates or bypassing agent infusion using the same negative binomial model as used for the primary analysis, which only includes treated bleeding episodes.

Time to first bleeding event

The time to first treated bleeding event in the treatment period will be calculated as the number of days between Day 1 and the onset date of the first treated bleeding event during the treatment period. The patient will be censored at the earlier of (Day 246, date of first intercurrent event) if no treated bleeding event has occurred. The time to first treated bleeding event in the efficacy period will be calculated similarly from Day 29 as the start of efficacy period. If a patient does not have bleeding episode data collected after Day 28 due to early study discontinuation, the time to first treated bleeding event in the efficacy period will be imputed from Day 1 as in the treatment period.

The time to first treated spontaneous bleeding event will be calculated similarly.

The proportion of patients who are bleeding free at the end of study (Month 9) will be estimated using the Kaplan-Meier method and compared using a Cox proportional hazards (PH) regression model with robust variance estimation and the treatment arm and the randomization strata of number of bleeding episodes in the 6 months prior to study entry as fixed effects. Plots of cumulative mean functions for the number of treated bleeds in the efficacy period and treatment period will be provided.

Symptoms related to bleeding

Descriptive statistics will be provided for symptoms related to bleeding events by each treatment arm.

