6.3 Efficacy Analysis

Bleeding Episode Definitions

The primary source of bleeding data will be the eDiary. Additional bleeding data may be captured from the bleeding diary pages of the CRF, if not reported in the eDiary. Any other sources of bleeding data will be discussed in the CSR.

A bleeding episode is defined as any occurrence of hemorrhage that may require administration of BPA or factor. Bleeding episodes sustained during sports and recreation will be counted as traumatic bleeding episodes.

Bleeding or any symptoms of bleeding at the same location that occur within 72 hours of the last injection used to treat a bleed or 72 hours after an untreated bleed at that location will be considered a part of the original bleeding event, and will count as one bleeding episode. Any bleeding symptoms that begin more than 72 hours from the last injection used to treat a bleed or 72 hours after an untreated bleed at that location will constitute a new bleeding event.

Traumatic bleeds that occur in different locations simultaneously (same date/time) in the same patient will be considered as one bleeding episode. Spontaneous bleeds that occur simultaneously (same date/time) in different locations in the same patient will be considered as separate bleeds.

Efficacy analysis will focus on observed data as collected, unless otherwise specified. Patients who discontinue study drug during the study will be strongly encouraged to continue study participation including the recording of bleeding episode data. Only bleeding episodes that are treated with BPA/factor will be included in the primary analysis of endpoints evaluating bleeding.

Efficacy Period and Treatment Period

In the protocol, for the purpose of ABR calculation, fitusiran “Onset Period”, “Efficacy Period” and “Treatment Period” are defined. The Onset Period is defined as the first 28 days after the first dose of fitusiran, during which the AT lowering capacity of fitusiran is increasing but has not yet reached therapeutic levels. The Efficacy Period is defined as starting on Day 29 when the AT lowering capacity of fitusiran has achieved therapeutic target range. The Treatment Period is defined as the onset period plus the efficacy period. The window for each period is modified and summarized in the table below. The corresponding window is applied to on-demand arm for analysis purpose.

Fitusiran arm/On-demand arm	
Onset Period	Day 1 to the earlier of Day 28 and the last day of bleeding follow up

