Efficacy Period	Day 29 to the earliest of (Day 246, or the last day of bleeding follow up)
Treatment Period	Onset period plus the efficacy period

The last day of bleeding follow up is defined as the deactivation date captured in eDiary.

If a patient does not have bleeding episode data collected after Day 28 due to early study discontinuation, the efficacy period will be from Day 1 to the earlier of date of study discontinuation and the last day of bleeding follow up.

The onset period, efficacy period and treatment period also exclude the period of following intercurrent events to avoid confounding of treatment effect for the primary efficacy analysis based on On-Treatment Strategy.

- After one month (28 days) from fitusiran treatment discontinuation in the fitusiran efficacy period. Excluding bleeding data after one month from fitusiran treatment discontinuation is considered reasonable and adequate considering that fitusiran is dosed monthly and EOS is one month after last dose of fitusiran
- Perioperative period of major surgery. The perioperative period is defined as the day of the surgery through the final day on which supplemental hemostatic or antithrombotic treatments are administered as part of the perioperative treatment plan.
- Period of minor surgery is defined as the Perioperative period of surgery above or to 72 hours from the end of surgery, whichever is later.
- Period of Antithrombin treatment is defined as the first day of antithrombin treatment through the final day on which antithrombin or other anticoagulant therapies are administered plus 5 half-lives of that specific product.
- After prophylactic treatment with emicizumab, BPA or factor.

The summary statistics for number of patients who are lost-to-follow-up and who had each intercurrent event will be provided.

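### The time-to-first-bleed censoring rule leaves out the last day of bleeding follow-up, so read literally it counts unobserved bleed-free time, mainly in the on-demand arm (exploratory, small effect)

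*SAP*

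**What the plan says.** SAP 6.3.1.3 (Time to first bleeding event) counts days from Day 1 to the first treated bleed during the treatment period. For patients without one it says: "The patient will be censored at the earlier of (Day 246, date of first intercurrent event) if no treated bleeding event has occurred". The efficacy-period and first-spontaneous-bleed versions are to be calculated similarly. The outputs are a Kaplan-Meier bleed-free proportion at Month 9 and a Cox comparison of the arms.

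SAP 6.3 defines the periods with an end-of-observation term:

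- The onset period stops at Day 28, or when bleeding follow-up ends if that comes sooner.
- The efficacy period is given as "Day 29 to the earliest of (Day 246, or the last day of bleeding follow up"). The treatment period is the sum of the two.
- Patients with no bleeding data after Day 28 because they left the study: "the efficacy period will be from Day 1 to the earlier of date of study discontinuation and the last day of bleeding follow up".
- "The last day of bleeding follow up is defined as the deactivation date captured in eDiary".

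The intercurrent events in SAP 6.3 are fitusiran discontinuation, major surgery, minor surgery, antithrombin treatment, and prophylaxis with emicizumab, BPA or factor. The first is worded "After one month (28 days) from fitusiran treatment discontinuation in the fitusiran efficacy period". Loss to follow-up is named beside the list, not in it: "The summary statistics for number of patients who are lost-to-follow-up and who had each intercurrent event will be provided".

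**The concern.** A patient is at risk in a time-to-event analysis only while bleeds can be recorded. The censoring rule has two terms, and neither is the end of the diary. Leaving the study is not an intercurrent event, and the discontinuation event has no on-demand counterpart. The literal result therefore differs by arm:

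- **On-demand:** a patient who leaves early without a bleed or a listed event is censored at Day 246, although nothing was recorded after the diary was deactivated.
- **Fitusiran:** a leaver is censored at about 28 days after stopping, so is carried at most about 28 days past leaving.

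At stake are the Month 9 bleed-free proportions and the hazard ratio. Both could include bleed-free time that nobody observed, most of it in the on-demand arm.

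**Working it through.** **The plan's own figures.** The documents give no figure for time to first bleed, so the check starts from SAP 5.1: ABR mean 18 (SD 14) on demand, mean 4 (SD 6) on fitusiran, 14 and 28 evaluable patients, 20% drop-out, 54 randomized.

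- Sample size: 42 / 0.8 = 52.5, so 53, or 54 at 2:1 (18 + 36). Reproduced.
- Power: SE of the log rate ratio = √[(14/18)²/14 + (6/4)²/28] = 0.352; |ln(4/18)| / 0.352 = 4.28; 4.28 − 1.96 = 2.32, a power of 0.99. This agrees with the stated figure of more than 90%.

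**First-bleed model.** Patient bleeding rates follow a gamma distribution and bleeds occur at a constant rate within a patient. With t = 246/365.25 = 0.6735 years, the dispersion k solves SD² = mean/t + k·mean²:

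- On-demand: k = (196 − 26.73)/324 = 0.522.
- Fitusiran: k = (36 − 5.94)/16 = 1.88.

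The bleed-free proportion at time d (in years) is S(d) = (1 + k·mean·d)^(−1/k). At Day 246:

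- On-demand: 7.33^(−1.914) = 2.2%.
- Fitusiran: 6.06^(−0.532) = 38.3%.

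These are the values that correct censoring estimates.

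**On-demand arm, literal rule.** Surgery, antithrombin treatment and prophylaxis are set aside. Nobody is then censored before Day 246, so Kaplan-Meier reduces to the plain proportion with no recorded bleed:

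0.8 × S(246 days) + 0.2 × (mean of S over the leaving times).

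For leaving times uniform between a and b (in years), that mean is [(1 + k·m·a)^(1−1/k) − (1 + k·m·b)^(1−1/k)] / [m(1 − k)(b − a)], where m is the mean ABR. Each leaver's chance of being bleed-free feeds the expected number affected, 18 × 0.2 × mean S, and the chance of at least one, 1 − (1 − 0.2 × mean S)^18.

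| Leaving times (assumed) | Mean S at leaving | Literal estimate | Affected of 18 | Chance of ≥1 |
|---|---|---|---|---|
| Uniform over 246 days | (1 − 0.162)/5.79 = 0.145 | 0.0177 + 0.0290 = 4.7% | 0.52 | 41% |
| All in first 82 days | (1 − 0.354)/1.93 = 0.335 | 0.0177 + 0.0669 = 8.5% | 1.20 | 71% |
| All in last 82 days | (0.221 − 0.162)/1.93 = 0.0305 | 0.0177 + 0.0061 = 2.4% | 0.11 | 10% |

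With uniform timing, 10% or 30% drop-out gives 3.4% or 5.9%, and a 23% or 55% chance of at least one.

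A single case shows the mechanism. If 17 of 18 patients bleed by Day 150 and one leaves bleed-free on Day 40, the correct Kaplan-Meier estimate at Day 246 is 0; the literal rule gives 1/18 = 5.6%.

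**Fitusiran arm, literal rule (simulated, uniform timing).** The SAP does not say plainly whether the 28 days run from the last dose or from leaving. Anchored at last dose + 28 days, the estimate moves from 38.3% to about 38.7%. Anchored at leaving + 28 days, it moves to 39.1%.

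**Hazard ratio (simulated trials of 18 versus 36, Cox model with treatment only).**

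- Cap at leaving + 28 days, 6,000 trials: median 0.237 correct, 0.258 literal. With early drop-out it is 0.236 and 0.290; with late drop-out it is unchanged at 0.237.
- Cap at last dose + 28 days, 600 trials, uniform timing: 0.234 and 0.259. The share of trials with p < 0.05 goes from 99.2% to 98.5%.

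**Efficacy-period version (clock from Day 29; from Day 1 for those who leave by Day 28).** On-demand is 2.7% correct and 6.3% literal (2.9% to 11.9% across the same timings), with 0.75 of 18 affected. The documents give no planning rate for spontaneous bleeds, so that version is not sized. A lower rate would leave more leavers bleed-free.

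**The case against.** The strongest reply is that the text around the formula already supplies the end date. The variable is defined within the treatment period, SAP 6.3 ends that period at the last day of bleeding follow-up, and the general default is "Efficacy analysis will focus on observed data as collected, unless otherwise specified". On that reading Day 246 is simply the nominal end for completers, and a careful programmer would not keep a departed patient at risk.

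Much of this stands as evidence of intent, but it does not close the gap. The treatment-period wording settles which bleeds count as events, while the censoring sentence gives its own date for patients without one. The default yields where something else is specified, and an explicit formula can be read as doing that. Two programmers could build different datasets.

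It is also fair that the consequence is slight. The 20% is a sample-size allowance, not a forecast of bleed-free withdrawals, and under uniform timing most trials (59%) would have no affected on-demand patient.

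A reader might infer two stronger points that the documents do not support:

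- **That the formula contradicts every related passage.** It omits one term. It agrees with the period table for anyone followed to Day 246 or with an earlier intercurrent event, and the rule for patients without data after Day 28 shows intent rather than a further contradiction.
- **That fitusiran stops before Day 29 escape the 28-day cap,** because that event is worded as falling in the efficacy period. This is a strained reading. Dosing starts on Day 1, so any stop plus 28 days falls on Day 29 or later, and the phrase can simply locate the excluded time. The lead-in also applies the exclusions to all three periods.

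**Conclusion.** The point holds as a minor defect of specification. The written censoring rule omits the end of bleeding follow-up. Followed literally, it would about double a small on-demand bleed-free proportion, from 2.2% to about 4.7% (2.4% to 8.5% by drop-out timing). It moves the fitusiran estimate by less than one percentage point and the median hazard ratio from about 0.24 to 0.26.

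These sizes rest on the planning means and SDs, 20% drop-out that is equal by arm and unrelated to bleeding, assumed leaving times, no other intercurrent events, and a Cox model without the stratum term.

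A reader might suspect that the rule flatters fitusiran or reaches the main result. Neither follows. The error favours the on-demand arm, so it is conservative for fitusiran. The analysis is exploratory and outside the testing hierarchy in SAP 5.7. The ABR analyses take their offset from the period definitions, so the primary result, alpha and power are unaffected.

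**What to change.** Amend the sentence in SAP 6.3.1.3 so that a patient without a treated bleed is censored at *the earliest of Day 246, the last day of bleeding follow-up, and the date of the first intercurrent event*. Apply it to the treatment-period, efficacy-period and spontaneous-bleed versions. For the efficacy-period version in patients with no data after Day 28, use the end date that SAP 6.3 already gives for them; that rule need not be carried into the treatment-period version.

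The cost is one phrase. No new data are needed, because the last day of bleeding follow-up is already defined as the eDiary deactivation date. One small downside should be stated: censoring there assumes that leaving is unrelated to bleeding risk. That is similar to the missing-at-random assumption stated in SAP 6.3.1.2 for the treatment policy analysis.

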6.3.1.4 Subgroup Analysis

The on-treatment and treatment policy efficacy analyses for the primary endpoint and the secondary endpoints based on bleeding episodes will be repeated for the following subgroups:

- Hemophilia type (Type A vs B)
- Number of bleeding episodes during the 6 months prior to study (≤ 10 vs > 10)

- Age group, years (<18, 18-64, ≥ 65)

In addition, region- and/or country-specific analyses will be performed to support regulatory submission as needed.

Negative binomial regression model will be applied only for subgroups that have at least 3 patients in each treatment arm and the model converges. Otherwise, only summary statistics will be presented.

6.3.2 Secondary Endpoints

6.3.2.1 ABR in the treatment period (Global Protocol), ABR in the efficacy period (US Protocol)

Analysis will include all bleeding episode data in the specified period. The on-treatment and treatment policy efficacy analyses will be repeated with this endpoint.

6.3.2.2 Annualized spontaneous bleeding rate in the efficacy period

Analysis will include spontaneous bleeding episodes occurring in the efficacy period. The on-treatment and treatment policy efficacy analyses will be repeated with this endpoint.

6.3.2.3 Annualized joint bleeding rate in the efficacy period

Analysis will include joint bleeding episodes occurring in the efficacy period. The on-treatment and treatment policy efficacy analyses will be repeated with this endpoint.

6.3.2.4 Haem-A-QoL

The Haem-A-QoL will be provided to patients ≥17 years of age, and includes 46 items contributing to 10 QoL domains (physical health, feelings, view of yourself, sports and leisure, work and school, dealing with hemophilia, treatment, future, family planning, partnership and sexuality). Scoring for each item is based on a 5-point Likert scale (never, rarely, sometimes, often, and all the time), and higher scores represent greater impairment. The change from baseline in physical health score and total score of Haem-A-QoL at the end of the study will be analyzed using an analysis of covariance (ANCOVA) model with fixed effects of treatment arm and the randomization strata of number of bleeding episodes in the 6 months prior to study entry (≤10 vs >10), baseline Haem-A-QoL physical health score and total score, as covariates. Least square means of the physical health score and total score in each treatment arm and the difference of the least square means of the physical health score and total score in the two arms (along with the 95% CI and p-value) will be presented. The normality assumption based on ANCOVA model will be examined and a sensitivity analysis based on the non-parametric Wilcoxon-Mann-Whitney test will be performed. Domain scores, standardized scale scores, and transformed scale scores for Haem-A-QoL and their changes from baseline will be summarized. The above ANCOVA analysis is based on observed data. For patient with missing assessment due to early withdrawal, a sensitivity analysis will also be performed by imputing the domain score and total score as the worst score if the reason of withdrawal is treatment-related in the corresponding treatment arm, and as the average score for other reasons of withdrawal that are not treatment related in the corresponding treatment arm. The same analysis as main will be performed as a sensitivity analysis by excluding values of those who completed Haem-A-QoL at baseline after first dose of fitusiran.

To evaluate the impact of Covid-19, the same ANCOVA model will also be repeated on Covid-19 unaffected set. In addition, a sensitivity analysis using same ANCOVA model will be performed excluding the data impacted by Covid-19 major/critical protocol deviation. A supportive analysis will be repeated on the patients whose responses level to EQ-5D dimensions “anxiety/depression” is no change or improved from baseline.

To evaluate the association between the change in Haem-A-QoL and other clinical measures, the analysis of change from baseline in the Haem-A-QOL physical health score and total score will be stratified by ABR level (0, >0 to <=5, >5) and concomitant pain medication use (Y, N). The ABR level is based on on-treatment strategy during the efficacy period.

The summary of adherence with Haem-A-QOL measurement will also be provided.

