5 GENERAL STATISTICAL METHODS

5.1 Sample Size Justification

Assuming a mean ABR of 18 with standard deviation (SD) = 14 in the on-demand arm (patients randomized to receive on-demand bypassing agents) and a mean ABR of no more than 4 with SD = 6 in the fitusiran treatment arm (patients randomized to receive fitusiran) in either the efficacy period or treatment period, with a sample size of 14 evaluable patients in on-demand arm and approximately 28 evaluable patients in the fitusiran treatment arm, it is projected that the study will have greater than 90% power for testing treatment difference in mean ABRs. This power estimation was based on negative binomial regression model with a 2-sided type I error rate of 0.05.

The planned sample size is 54 randomized patients assuming a 20% drop-out rate.

In the China Addendum #1 to protocol amendment 2, it specifies that before any Chinese patients are randomized to receive 80 mg of fitusiran subcutaneous (SC) treatment, three (3) subjects in China will be enrolled into a China specific non-randomized fitusiran treatment arm to receive fitusiran as a SC injection administered every 4 weeks, with initial starting dose of 50 mg SC. After the observation period for these 3 patients is completed and dose escalation is authorized by the Sponsor, the 3 patients will undergo dose escalation to receive 80 mg of fitusiran as a SC injection every 4 weeks. These 3 patients will not be included in the ITT Set for the efficacy analyses but will be included in the Safety Set for the safety analyses. Their efficacy data will be included in separate listings.

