5.7 Multiple Comparisons/Multiplicity

To control for the familywise error rate at 0.05 level in the testing of primary and selected secondary endpoints, a hierarchical testing approach will be used. The endpoints will be tested in the following order:

Global protocol	US protocol	2-Sided alpha
1. ABR in the efficacy period	1. ABR in the treatment period	0.05
2. ABR in the treatment period	2. ABR in the efficacy period	0.05
3. Annualized spontaneous bleeding rate in the efficacy period		0.05
4. Annualized joint bleeding rate in the efficacy period		0.05
5. Change in Haem-A-QOL physical health score and total score in the treatment period		0.05

If testing of any of the endpoints is not statistically significant, formal testing of subsequent endpoints will stop and the null hypothesis for subsequent tests will not be rejected. For endpoint 5, change in Haem-A-QOL physical health score in the treatment period will be tested first followed by change in Haem-A-QOL total score in the treatment period. The testing of the secondary endpoint ABR in the onset period will not be included in this hierarchical testing procedure.

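### The normality check on the Haem-A-QoL ANCOVA also drops the stratum and the baseline covariate, so a disagreement between the two tests cannot be put down to non-normality

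*SAP*

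**What the plan says.** SAP 6.3.2.4 takes as response "The change from baseline in physical health score and total score of Haem-A-QoL at the end of the study". The main model is an ANCOVA with "fixed effects of treatment arm and the randomization strata of number of bleeding episodes in the 6 months prior to study entry", and with "baseline Haem-A-QoL physical health score and total score, as covariates" (read here as the matching baseline score for each endpoint).

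The same section says that the normality assumption will be examined and that "a sensitivity analysis based on the non-parametric Wilcoxon-Mann-Whitney test will be performed". It names no stratum, covariate or stratified version. The version 2 entry in the SAP 2.6 change log gives the same bare name. Neither document mentions a van Elteren test, a rank ANCOVA or any other adjusted rank test.

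Where 6.3.2.4 wants the main model kept in a sensitivity analysis, it says so: the Covid-19 checks and the check on questionnaires completed after the first dose are tied explicitly to the main ANCOVA.

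The endpoint is under alpha control. It is step 5 of the fixed sequence in SAP 5.7, at two-sided 0.05: "For endpoint 5, change in Haem-A-QOL physical health score in the treatment period will be tested first", and the total score follows.

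**The concern.** A check on one assumption should relax that assumption and hold the rest of the analysis fixed. This one replaces a normal-theory test by a rank test and also removes the baseline covariate and the factor on which randomisation was stratified. If the ANCOVA is significant and the Wilcoxon is not, the reader cannot tell whether the ANCOVA leaned on a false normality assumption or the second test simply had less power. The SAP gives no rule for reading such a disagreement.

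The sample is small and allocation is 2:1, so the lost precision is not negligible. What is at stake is the robustness statement for a confirmatory secondary endpoint.

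**Working it through.** **The plan's own figures.** The SAP gives no power, effect size or SD for Haem-A-QoL. Its sample size rests on bleeding: "Assuming a mean ABR of 18 with standard deviation (SD) = 14 in the on-demand arm", "a mean ABR of no more than 4 with SD = 6 in the fitusiran treatment arm", 14 and 28 evaluable patients, and a "negative binomial regression model with a 2-sided type I error rate of 0.05". This reproduces. SE of the log rate ratio = √(14²/(14·18²) + 6²/(28·4²)) = 0.352; |ln(4/18)| = 1.504; power = Φ(1.504/0.352 − 1.960) ≈ 99%. A weighted common dispersion gives about 95%, against the stated more than 90%. For dropout, 42/0.8 = 52.5; by arm 18 and 35, rounded to 18 + 36 = 54 for 2:1.

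**Patients in this analysis.** Of 54 patients about 5 are adolescents (Protocol 4.3), and Haem-A-QoL goes to those aged 17 or over. That leaves about 49. The questionnaire is not collected at the early-termination visit (Protocol Table 1, footnote s), and 20% dropout is planned: 49 × 0.8 ≈ 39, or 26 and 13 at 2:1. A few 17-year-olds could add to this.

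**Analytic size of the loss.** With equal variances and correlation ρ between baseline and end of study, the change score has variance 2(1−ρ)σ² and the ANCOVA residual (1−ρ²)σ². The ratio of the second to the first is (1+ρ)/2. Under normality the Wilcoxon costs a further factor 3/π = 0.955.

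| ρ | (1+ρ)/2 | × 3/π | Wilcoxon power when ANCOVA has 80% |
|---|---|---|---|
| 0.3 | 0.65 | 0.62 | 60% |
| 0.5 | 0.75 | 0.72 | 66% |
| 0.7 | 0.85 | 0.81 | 71% |
| 0.9 | 0.95 | 0.91 | 76% |

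The last column is Φ(2.802·√RE − 1.960), where RE is the third column and 2.802 = 1.960 + 0.842.

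**Simulation.** 13 against 26 patients, 800 trials per row, Monte Carlo standard error about 1.5–1.8 points. End score = ρ·baseline + √(1−ρ²)·error + stratum effect − δ·arm, in SD units, with about half of each arm in each stratum. δ = 2.802·√(1−ρ²)·√(1/13 + 1/26); for example 0.824 at ρ = 0.5. Normal errors, percentages of trials:

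| ρ | Stratum effect (SD) | ANCOVA | Wilcoxon on change | van Elteren | Rank ANCOVA | ANCOVA significant, Wilcoxon not |
|---|---|---|---|---|---|---|
| 0.3 | 0 | 75.4 | 58.1 | 57.9 | 68.2 | 20.5 |
| 0.3 | 0.5 | 76.1 | 51.8 | 56.4 | 69.1 | 26.5 |
| 0.5 | 0 | 76.1 | 60.9 | 59.8 | 69.6 | 19.2 |
| 0.5 | 0.5 | 77.1 | 55.9 | 61.0 | 71.6 | 22.8 |
| 0.7 | 0 | 75.5 | 67.4 | 65.8 | 71.6 | 12.2 |
| 0.7 | 0.5 | 77.9 | 61.1 | 68.6 | 72.5 | 18.2 |
| 0.9 | 0 | 77.2 | 71.9 | 72.0 | 71.9 | 8.0 |
| 0.9 | 0.5 | 78.1 | 56.8 | 72.1 | 72.0 | 21.4 |

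Rank ANCOVA here means ranks of change, with ranked baseline and stratum regressed out, and the residuals then compared within strata. A repeat simulation of the same setting gave ANCOVA 76–78%, Wilcoxon 54–70%, rank ANCOVA 72–75% and discordance 8–26%. With all 54 patients (18 and 36) discordance was 6–24%.

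**Size under the null** (ρ = 0.5, stratum effect 0.5 SD, 1,500 trials): ANCOVA 4.7%, Wilcoxon 3.0%, van Elteren 4.5%, rank ANCOVA 4.5%.

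**Heavy tails** (t with 3 df, 13 against 26, no stratum effect), at ρ = 0.3, 0.5, 0.7 and 0.9: ANCOVA 78.4, 82.6, 83.1, 81.5; Wilcoxon 67.5, 78.8, 85.4, 91.9; rank ANCOVA 88.1, 90.1, 90.5, 92.2. **Skewed errors** (lognormal, no stratum effect, ρ = 0.5, 0.75, 0.9): Wilcoxon 86–97% against ANCOVA 82–83%.

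**The case against.** The strongest reply is that nothing confirmatory depends on this test. That stands. A reader might infer that the Wilcoxon takes over if normality fails, or that it can halt the sequence. The documents do not support this: 6.3.2.4 runs it unconditionally as a sensitivity analysis, and SAP 5.7 gives it no role. The ANCOVA remains the formal test.

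The second reply is that the test is valid. That also stands. It does not inflate type I error, and with a stratum effect it is conservative (3.0%). Any error works against the sponsor's claim.

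Third, a reader might infer that dropping the covariate carries a chance baseline imbalance into the comparison in full. It does not. A change score already subtracts baseline, so an imbalance d shifts the expected change by (1−ρ)d: 60%, 40% and 25% of d at ρ = 0.4, 0.6 and 0.75.

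Fourth, the check exists for non-normal data, and there the Wilcoxon can beat the ANCOVA, as the heavy-tailed and skewed runs show. So it would be wrong to say that a non-significant Wilcoxon is merely lost efficiency; that reading fits near-normal data. The narrower point survives: in the normal and heavy-tailed runs shown above, rank ANCOVA was never below the plain Wilcoxon, though the two are level at ρ = 0.9 without a stratum effect.

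Finally, that the test is unadjusted is inferred from the SAP's silence, and the SAP does not say outright whether it is applied to change scores or to residuals. The change log points to change scores.

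**Conclusion.** The point holds as a matter of interpretation and is modest in weight. The named rank test drops the stratum and the baseline covariate along with the normality assumption, so it cannot isolate the question it was added to answer. Under normal errors, where the ANCOVA is sound, the two tests would still disagree in the ANCOVA's favour in roughly 8–26% of trials. Plain Wilcoxon power is about 54–70%, against about 76–78% for ANCOVA and 72–75% for rank ANCOVA.

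These sizes rest on assumptions that are not in the documents: 26 and 13 adults with end-of-study scores, a correlation of 0.3–0.9, a stratum effect of 0 or 0.5 SD, and a true effect set for nominal 80% ANCOVA power. The loss is small when the correlation is near 0.9 and the stratum has no effect. Severity: consider.

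**What to change.** In SAP 6.3.2.4, replace the Wilcoxon-Mann-Whitney test by a rank ANCOVA for each score: ranks of the change from baseline, adjusted for the ranked baseline value of that score and for the randomisation stratum. The unadjusted Wilcoxon may stay as a descriptive result. It would help to add that the ANCOVA remains the formal test whichever way the rank analysis falls.

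A van Elteren test is not a sufficient substitute, because it restores the stratum only. At ρ = 0.5 with a 0.5 SD stratum effect it reaches 61%, against 56% for the plain Wilcoxon and 72% for rank ANCOVA. With no stratum effect it gains nothing.

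The cost is one further line of analysis code. The rank test gives no direct estimate of the treatment effect, so the least-squares mean difference and its interval still come from the ANCOVA. No new data are needed, and the SAP provides for changes before database lock.
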